#### Repeat Cycle and Observation Cohorts

Once the last subject in the expansion cohort has been enrolled and safety of the maximum safe and feasible dose is confirmed, approximately 6 additional subjects, who fulfil the criteria for the clinical diagnosis of CM, but without documented growth, will be enrolled into an observation cohort (Cohort 10). These subjects will be assessed every 3 months (ie, 90 day (+/- 7 days) intervals from the Screening Visit) until tumor growth of the CM lesion is established (as defined in Protocol Section 8.3.4.) and at which time will then receive treatment with AU-011, as 3 repeat 80 µg doses, each followed by 2 repeat laser applications and move to the same visit schedule as subjects entering the trial and receiving treatment with AU-011 immediately. These subjects will receive Cycle 2 of AU-011 administered as 3 repeat 80 µg doses, each followed by 2 repeat laser applications no earlier than the Week 12 Visit and after resolution of any inflammation resulting from the first cycle or when the inflammation is minimal and decreasing based on investigator judgement. Cycle 2 should be administered as soon as reasonably possible after inflammation has resolved or is minimal and decreasing based on investigator judgement.

Confidential

In addition, approximately 6 additional subjects, who meet the criteria for a clinical diagnosis of CM, with or without documented growth, will enter Cohort 11 and receive two cycles of AU-011 treatment (each cycle will be comprised of 3 repeat 80 µg doses, each followed by 2 repeat laser applications). Cycle 2 of AU-011 will be administered as 3 repeat 80 µg doses, each followed by 2 repeat laser applications no earlier than the Week 12 Visit and after resolution of any inflammation resulting from the first cycle or when the inflammation is minimal and decreasing based on investigator judgement. Cycle 2 should be administered as soon as reasonably possible after inflammation has resolved or is minimal and decreasing based on investigator judgement.

The intention is to alternate the enrolment of Cohorts 10 and 11. If during the enrollment of these subjects, a subject has just been enrolled into Cohort 11 and a subject with documented growth presents, then that subject may instead be enrolled into Cohort 11 rather than Cohort 10 for which they would not be eligible due to the presence of documented growth and instead will be assigned to receive the first of 2 cycles of AU-011.

If 2 subjects experience a DLT during treatment with Cycle 2, then no further subjects will receive Cycle 2 of AU-011 until discussed with the independent ocular oncologist and medical monitor and continuation of enrollment is confirmed.

#### Subjects with Documented Growth

Enrollment in Cohorts 10 and 11 was closed following approval of protocol revision 11 (Rev-11) at each site. An additional cohort, Cohort 12, of subjects with minimum defined levels of documented growth will be initiated to allow assessment of safety and efficacy of 2 cycles of AU-011 treatment in this key subgroup of subjects with CM. Since Cohort 12 has the same dose as Cohort 11, no additional safety review will be required prior to initiating this cohort.

Up to 15 subjects, who meet the criteria for a clinical diagnosis of CM with documented growth (as defined in Protocol Inclusion Criteria 5C) will enter Cohort 12 and receive two cycles of AU-011 treatment (each cycle will be comprised of 3 repeat 80 µg doses, each followed by 2 repeat laser applications). Cycle 2 of AU-011 will be administered as 3 repeat 80 µg doses, each followed by 2 repeat laser applications no earlier than the Week 12 Visit and after resolution of any inflammation resulting from the first cycle or when the inflammation is minimal and decreasing based on investigator judgement. Cycle 2 should be administered as soon as reasonably possible after inflammation has resolved or is minimal and decreasing based on investigator judgement.

If 2 subjects experience a DLT during treatment with Cycle 2, then no further subjects will receive Cycle 2 of AU-011 until discussed with the independent ocular oncologist and medical monitor and continuation of enrollment is confirmed.

### **3.3 Sample Size Justification**

No formal sample size calculation was performed for this ascending single and repeat dose and cycle phase 1b/2 study. Approximately 60 subjects with small primary CM will be enrolled and treated with Light-activated AU-011 at 3 dose levels and repeat dose regimens and cycles of Light-activated AU-011 and one or two laser applications.

The study was designed to investigate at least 3 subjects at each treatment level and expand to investigate an additional 6 subjects at the maximum feasible dose. Provisions for expanding cohorts based on observed DLTs were also provided as per the study design section above.

Confidential

## 4 General Analysis Definitions

Data will be analyzed using SAS (Version 9.4 or later).

No tests of significance will be carried out to compare cohorts on baseline data because any observed differences between them must be attributed to chance.

Since this is an exploratory study, no formal hypothesis testing will be performed. Descriptive statistics will be used to tabulate and summarize baseline, efficacy and safety outcomes.

Descriptive statistics will be tabulated as follows:

- Categorical data will be summarized in contingency tables presenting frequencies and percentages.
- Continuous data will be summarized using number of non-missing values (n), mean, standard deviation, median, minimum and maximum values.

The tables will be created by cohort and overall, in the order as listed in Section 4.5.4. In addition, a subtotal of dose escalation cohorts (Cohort 1 to 8) and a subtotal of the expansion cohorts (Cohort 9 to 12) will be included in all the relevant tables.

Listings with individual values will be provided for all data presented in the tables.

### 4.1 Study Period and Visit Window Definitions

#### 4.1.1 Study Periods

The study consists of 3 periods: screening, active period and follow-up period. Results will be presented by visit and not by period.

#### 4.1.2 Visit Windows

The schedule of study assessments can be found in Appendix 11.1 of this SAP.

Missing scheduled visit will be substituted by an unscheduled or early withdrawal visit occurring within each follow-up visit window. If there are multiple unscheduled or early withdrawal visits occurring within the window, the closest one within the visit window will be used. If no unscheduled or early withdrawal visit occurred within the window, the visit will be considered as missing. The details are tabulated in Appendix 11.2.

An exception to this visit-window algorithm is the analysis of the "Last Visit". For all "Last Visit" time-point analyses, a subject's last non-missing endpoint assessment will be used for the analysis, regardless of if the visit falls within a particular visit window or not.

### 4.2 Planned analyses

Two interim analyses are planned: 1) after the first 2 cohorts (SAD cohorts) have completed 12 months of follow-up (Visit 14); and 2) after all subjects complete Week 12 visit (Visit 11).

The final analysis will be performed when all enrolled subjects will have completed the End of Study visit or the Early Termination visit, if early discontinued from study.

Note on SAP V2.0:

- 1) One interim analysis was performed for the '01AUG2018 Deliverable'.
- 2) No further interim analyses are going to be done.
- 3) Due to the early termination of the study, the final analysis will be performed after all subjects complete the Week 52 Visit.

Confidential

## 4.3 Definition of Populations

### 4.3.1 Intention-To-Treat Population

The Intention-To-Treat (ITT) population will consist of all enrolled subjects, whether or not they receive one administration of study treatment.

This is the primary population for the efficacy analysis.

### 4.3.2 Efficacy Evaluable Population

The Efficacy Evaluable population will consist of ITT population subjects, excluding subjects from site 009, who have been excluded based on site audit findings.

This population will be used as a sensitivity analysis for efficacy.

### 4.3.3 Safety Population

The Safety population will include all subjects who received at least one administration of study treatment. Subjects will be analyzed according to the treatment that they actually received.

This is the primary population for the safety analysis.

## 4.4 Subgroup Definitions

The following subgroups are defined for additional characterization of efficacy and/or safety of AU-011:

- Subjects with documented growth (DG): defined as subjects who had any amount of documented growth on tumor thickness
- Phase 3 Eligible (Ph3 Elig): defined as subjects with entry criteria similar to planned phase 3 criteria
  - Subjects with tumor thickness of  $\geq 0.5$  mm and  $\leq 3.0$  mm on B-scan ultrasound, a largest basal diameter of  $\leq 13.0$  mm on fundus photos with an estimated tumor volume  $\leq 50$  mm^3 and tumor growth of  $\geq 0.3$  mm on tumor thickness within 2 years of screening
- Phase 3 Eligible Therapeutic Regimen at 2 cycles (Ph3 Elig TR2C)
  - Phase 3 Eligible subjects who received 2 cycles of AU-011 treatment, each cycle comprised of three weekly treatments with 80 $\mu$ g x 2 laser applications
- Phase 3 Eligible - High Risk for Vision Loss (Ph3 Elig HRVL)
  - Phase 3 Eligible subjects with tumor  $\leq 3.0$  mm from the fovea or optic disc

## 4.5 Treatment Assignment and Treatment Cohorts

### 4.5.1 Description of Study Drug

Light-activated AU-011 is a combination product consisting of a drug (AU-011) and a laser (Aura Photoactivation system) that delivers 689 nm light to activate the drug once it is bound to the tumor cells. AU-011 drug substance is a modified human papillomavirus-derived, empty viral like particle (VLP) conjugated to approximately 200 molecules of a phthalocyanine-based photosensitizer IRDye®700DX. AU-011 drug product is a sterile, pale blue aqueous solution supplied at a concentration of 0.4 mg per mL of buffered isotonic solution (pH 6.5). AU-011 is supplied in a [REDACTED] mL, high density plastic, single-use vial; each vial contains a fill volume of [REDACTED] mL.

Confidential

#### 4.5.2 Administration of AU-011

In this clinical trial, AU-011 study drug will be administered by IVT injection and will be followed by laser light application (689 nm) to the CM 6 to 8 hours after administration of AU-011. The maximum concentration of the current AU-011 formulation is 40 µg in [REDACTED] µl and as a result, the maximum feasible dose is 80 µg administered as [REDACTED] injections of 40µg in [REDACTED] µl.

AU-011 will be administered via IVT injection as a low dose (20 µg) per IVT injection ([REDACTED] µL injection), a medium dose (40 µg) per IVT injection ([REDACTED] µL injection), or a high dose (80 µg) per IVT injection ([REDACTED] µL injections with interim IOP assessment).

Subjects in cohorts 1 (20 µg single dose), 2 (40 µg single dose) and 3 (80 µg single administration given as [REDACTED] injections of 40 µg in [REDACTED] µl) will receive one treatment followed by a single laser application, subjects in cohort 4 (40 µg two repeat doses) will receive [REDACTED] injections one week apart followed by a single laser application, subjects in cohort 5 (40 µg three repeat doses) will receive [REDACTED] injections one week apart followed by a single laser application, subjects in cohort 6 (80 µg single dose followed by 2 laser applications) will receive a single dose administered as [REDACTED] injections of 40 µg in [REDACTED] µl followed by 2 laser applications, subjects in cohort 7 (80 µg three repeat doses followed by a single laser application) will receive 3 doses each administered as [REDACTED] injections of 40 µg in [REDACTED] µl one week apart followed by a single laser application, and subjects in cohorts 8 and 9 (80 µg three repeat doses followed by two laser applications) will receive 3 doses each administered as [REDACTED] injections of 40 µg in [REDACTED] µl one week apart followed by 2 laser applications. Subjects in cohorts 3, 6, 7, 8 and 9 receiving 80 µg doses given as [REDACTED] injections of 40 µg in [REDACTED] µl will have their IOP measured prior to and after each injection. IOP must be 21 mm Hg or less before each injection can be given and the maximum interval between the two injections is 2 hours. IOP must also be 21 mm Hg or less before the subject is discharged from the clinic.

Subjects enrolled in the observation cohort and after exhibiting tumor growth (Cohort 10), and repeat cycle cohorts (Cohorts 11 and 12) will receive 2 cycles of AU-011 at the highest feasible and tolerated dose of 3 repeat 80 µg doses, each followed by 2 repeat laser applications. The second cycle of AU-011 will be administered no earlier than the Week 12 Visit and after resolution of any inflammation resulting from the first cycle or when the inflammation is minimal and decreasing based on investigator judgement. Cycle 2 should be administered as soon as reasonably possible after inflammation has resolved or is minimal and decreasing based on investigator judgement. However, if 2 subjects experience a DLT during treatment with Cycle 2, then no further subjects will receive Cycle 2 of AU-011 until discussed with the independent ocular oncologist and medical monitor and continuation of enrollment is confirmed. If the fovea is within 2 mm of the tumor edge or edge of the clinical margin of the tumor, an adjustment to the laser procedure should be performed on each treatment day of both cycles (as outlined in the Protocol section 8.2.2).

#### 4.5.3 Laser Activation of AU-011

This study will use the Aura Photoactivation System which will deliver light at 689 nm to the CM 6 to 8 hours after the IVT administration (after the second IVT injection for the subjects receiving 80 µg doses) of study drug AU-011. A second laser application will also be investigated in this trial to ensure that maximum tumor cell necrosis occurs with each administration of Light-activated AU-011. The study procedures binder provides detailed instructions on the procedures for laser application for this study.

Confidential

#### 4.5.4 Treatment Cohorts

The treatment cohorts are defined as follow:

**Dose Escalation cohorts:**

- Cohort 1: 20 µg x 1 laser, Single
- Cohort 2: 40 µg x 1 laser, Single
- Cohort 3: 80 µg x 1 laser, Single
- Cohort 4: 40 µg x 1 laser, 2XQ. Wk
- Cohort 5: 40 µg x 1 laser, 3XQ. Wk
- Cohort 6: 80 µg x 2 lasers, Single
- Cohort 7: 80 µg x 1 laser, 3XQ. Wk
- Cohort 8: 80 µg x 2 lasers, 3XQ. Wk

**Expansion cohorts:**

- Cohort 9: 80 µg x 2 Lasers, 3XQ. Wk
- Cohort 10: Observational cohort - No documented growth
- Cohort 11: 2 Cycles of AU-011 – With or without documented growth
- Cohort 12: 2 Cycles of AU-011 – Documented growth

#### 4.6 Calculated Variables

- Study day 1 is defined as the day when first study treatment was received.
- The baseline is defined as the last assessment done before or on study day 1. For instance, if data was collected at screening and Day 1, then the Day 1 value will be used for baseline
- Time since diagnosis of CM (months) = (month and year of screening – month and year of diagnosis).

Assessments done on the date of study treatment administration are assumed to take place before the administration, unless specified otherwise.

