The first expansion cohort (Cohort 9) is designed to establish the preliminary efficacy of AU-011 delivered at the highest dose that is safe and well tolerated from the escalation phase of the trial. Cohort 10 is designed to provide estimates of growth rates in observation subjects and Cohort 11 is designed to demonstrate the safety and tolerability of administering two 3-week treatment cycles of AU-011. Cohort 12 is designed to evaluate the efficacy and safety of AU-011 in subjects with documented growth who are similar to the planned Phase 3 population.

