If subjects are discharged during daylight hours, appropriate sun protection, e.g., sunglasses and a hat, will be required.

Study subjects will be required to return for an ocular examination 24 hours ± 4 hours following intravitreal administration, followed by 11 visits (Day 8, Day 15, Day 29, Week 6, Week 8, Week 12, Week 26, Week 39, Week 52, Week 78, and Week 104). At these visits, subjects will be monitored with systemic and ophthalmic assessments. In addition, subjects in both the 2 and 3 repeat Light-activated AU-011 administration cohorts will have an additional safety visit on Day 9. Subjects in the 3 repeat Light-activated AU-011 administration cohort will have an additional safety visit at Day 16. Subjects in the observation cohort (Cohort 10) will be seen every 3 months (ie, 90 day (+/- 7 days) intervals from the Screening Visit) until tumor growth is established and then seen at the schedule described in Section 10 and Appendix 1 until the time of receiving Cycle 2, when they will then follow the schedule described in Appendix 4. Subjects in the observation cohort in whom tumor growth is not observed during the 2 year study period will exit the study at Week 104. Subjects in the repeat cycle of AU-011 cohorts (Cohorts 11 and 12) will also follow the schedule described in Section 10 and Appendix 1 until the time they receive the second cycle of AU-011, when they will then follow the schedule described in Appendix 4.

If the second cycle of AU-011 occurs after Visit 15 (Week 78), subjects will be followed for 26 weeks post-treatment and then may be rolled into the long-term follow-up study pending subject consent. Details regarding the follow-up visit schedule after the second cycle of AU-011 can be found in Appendix 4.

All subjects' study participation will be for a minimum of 2 years and all subjects in this study may then be rolled into the long-term follow-up study pending consent.

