nFor Single Light-activated AU-011 administration cohort and 2 Repeat Light-activated AU-011 administration cohort subjects, only study product and/or study procedure related AEs. For 3 Repeat Light-activated AU-011 administration cohort subjects, any AE.

oFor the observation cohort (Cohort 10) every 3 month visits (i.e. 90 day (+/- 7 days) intervals from the Screening Visit) prior to evidence of tumor growth, all procedures outlined for Visit 6 (Day 15) will be performed with the exception of OCTA and Anti-drug Antibody (ADA) testing which is not required.

pFor Cohort 6, 7, 8, and 9 subjects only

qFor Cohort 10, 11, and 12 subjects, all SAEs and AEs and concomitant medications will be reported from the time the subject signs the informed consent through their last study visit.

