## 11.2 Definition of Visit Windows in Reporting

The definition of visit label and visit windows in reporting are described in the table below.

Study Period	Visit Label	Definition [Day window]
Screening	Visit 1	= Subject screening date; nominally 1 to 28 days prior to the first AU-011 treatment. 'Day 1' - 'Date of assessment' = [1 to 28]. Alternatively, this is the assessment before the first treatment date.
Active Period	Visit 2 - D1 (Baseline)	= An assessment with the same date as recorded on the Day 1 Administration CRF Target date = 1
	Visit 3 - D2	= An assessment where 'Date of assessment' - 'Day 1' + 1 = 2 Target date = 2
	Visit 4 - D8	= An assessment where 'Date of assessment' - 'Day 1' + 1 = [8 - 9] Target date = 8
	Visit 5 - D9	= An assessment where 'Date of assessment' - 'Day 1' + 1 = [9 - 10] Target date = 9. Alternatively, this is the assessment one day after Visit 4 - D8.
	Visit 6 - D15	= An assessment where 'Date of assessment' - 'Day 1' + 1 = [15 - 16] Target date = 15
	Visit 7 - D16	= An assessment where 'Date of assessment' - 'Day 1' + 1 = [15 - 17] Target date = 16. Alternatively, this is the assessment one day after Visit 6 - D15.
Follow-up Period	Visit 8 - D29	= An assessment where 'Date of assessment' - 'Day 1' + 1 = [22 - 36] Target date = 29
	Visit 9 - W6	= An assessment where 'Date of assessment' - 'Day 1' + 1 = [37 - 50] Target date = 43
	Visit 10 - W8	= An assessment where 'Date of assessment' - 'Day 1' + 1 = [51 - 64] Target date = 57
	Visit 11 - W12	= An assessment where 'Date of assessment' - 'Day 1' + 1 = [65 - 113] Target date = 85
	Visit 12 - W26	= An assessment where 'Date of assessment' - 'Day 1' + 1 = [155 - 211] Target date = 183
	Visit 13 - W39	= An assessment where 'Date of assessment' - 'Day 1' + 1 = [246 - 302] Target date = 274
	Visit 14 - W52	= An assessment where 'Date of assessment' - 'Day 1' + 1 = [337 - 393] Target date = 365
End of Study	Visit 15 - W78	= An assessment where 'Date of assessment' - 'Day 1' + 1 = [463 - 631] Target date = 547
	Visit 16 - W104	= An assessment where 'Date of assessment' - 'Day 1' + 1 = [700 - 756] Target date = 728

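### The SAP plans no summary of Cohort 10's untreated observation period and gives its never-treated subjects no baseline, although the protocol enrols the cohort to estimate growth rates

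*SAP*

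**What the plan says.** **Purpose and conduct of the cohort.** The rationale in Protocol 4.6 states: "Cohort 10 is designed to provide estimates of growth rates in observation subjects". SAP 3.2 plans "approximately 6 additional subjects, who fulfil the criteria for the clinical diagnosis of CM, but without documented growth", seen every 90 (±7) days from Screening until growth is established. At these visits "all procedures outlined for Visit 6 (Day 15) will be performed with the exception of OCTA and Anti-drug Antibody (ADA) testing" (SAP 11.1, footnote o). Visit 6 includes B-scan and fundus photographs, so thickness and LBD are collected. Subjects who grow are then treated. Those "in whom tumor growth is not observed during the 2 year study period will exit the study at Week 104" (Protocol 6.1).

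**Analysis anchors.** SAP 4.6: "Study day 1 is defined as the day when first study treatment was received". It continues: "The baseline is defined as the last assessment done before or on study day 1". SAP 11.2 places screening "nominally 1 to 28 days prior to the first AU-011 treatment" (or, alternatively, at the assessment before first treatment) and counts all later windows from Day 1. Neither section makes an exception for Cohort 10.

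**Growth-rate analysis.** SAP 8.1.8 is the only one. It compares post-treatment with historical thickness growth in the SAP 4.4 subgroups, by MMRM, in a separate sponsor report. None of those subgroups is the observation cohort.

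**Populations.** ITT (SAP 4.3.1) takes in every enrolled subject, treated or not, and is primary for efficacy. SAP 4 adds a subtotal for Cohorts 9 to 12.

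**The concern.** The protocol gives this cohort one purpose, and following the SAP as written produces no answer to it. The word baseline also carries two meanings. Protocol 8.3.4 defines growth in Cohort 10 as an increase from a baseline that must come before the growth, whereas for a treated grower the SAP baseline comes after it.

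The gap also reaches the primary efficacy population. Never-treated Cohort 10 subjects belong to ITT, but the SAP does not say how they enter tables built on change since treatment. Two rules matter:

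- **Visual acuity (SAP 8.2).** A subject with no post-treatment acuity data is not a failure, and preservation means not failing. Read literally, a subject who was never treated counts as vision preserved.
- **Tumor response (SAP 8.1.1).** For Month 12 LOCF and Last Visit, a subject without post-baseline values takes the baseline value. If a programmer adopts Screening as baseline, an untreated subject can be classed as stable disease. If not, the response is undefined. The SAP leaves this open.

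**Working it through.** The plan has no figure to reproduce: SAP 3.3 reports no formal sample size calculation. The check applies the SAP's own day rules to the Cohort 10 schedule.

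**Number of observation visits.** Week 104 is 728 days and 728 / 90 = 8.09, so at most 8 visits, at days 90, 180, ..., 720 from Screening. With 6 subjects, 6 × 8 = 48 assessments. If observation is cut at Week 52 (assumption), 364 / 90 = 4.04, so 4 visits and 6 × 4 = 24.

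**A subject who grows and is treated.** Assume treatment starts 14 days after the visit that established growth, here day 360. Day 1 is then day 374 from Screening.

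| Assessment (days from Screening) | Days before Day 1 | In the 1–28 day screening window? |
|---|---|---|
| 0 | 374 | no |
| 90 | 284 | no |
| 180 | 194 | no |
| 270 | 104 | no |
| 360 | 14 | yes |

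Four of the 5 pre-treatment assessments have no window. With growth found at day 720 it is 8 of 9. Lags of 1 and 28 days give the same counts, and no observation visit ever falls in a post-baseline window. Baseline is the last scan before or on Day 1, so it already contains the growth.

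**A subject who never grows.** There is no first treatment and so no Day 1. Baseline, study day, change from baseline and every windowed visit are undefined, for up to 8 visits. The Last Visit rule in SAP 4.1.2 ignores windows and could pick up a value, but there is no baseline to compare it with.

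**Would re-anchoring Day 1 be enough?** With Screening as Day 1, the visits fall on days 91, 181, 271, 361, 451, 541, 631 and 721. Seven fall in existing windows (W12, W26, W39, W52, W78 twice, W104). Day 451 falls between W52 [337–393] and W78 [463–631]. Observation-specific windows are needed, and re-anchoring alone adds no growth-rate summary.

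**Possible effect on vision preservation.** Suppose all 6 are never treated and all 60 planned subjects are in ITT (a ceiling). If the preserved proportion in the other 54 is p, the reported proportion is (54p + 6) / 60 = p + 0.10 × (1 − p). The documents give no p. Assumed values of 0.5 to 0.9 give an inflation of 5 to 1 percentage points.

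**Precision of a mean growth rate.** The 95% half-width is t(0.975, n − 1) / √n × SD: 1.05 × SD for n = 6, 1.59 × SD for n = 4 and 2.48 × SD for n = 3. The documents give no SD.

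**Why a plain mean of slopes misleads.** Observation stops on growth. Under Protocol 8.3.4, a subject who qualifies at 90 days on the thickness growth-rate criterion needs at least 0.15 mm, a slope of 0.15 × 365 / 90 = 0.61 mm/year or more from a very short record. Averaging such slopes equally with two-year slopes from non-growers biases the mean upward.

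**The case against.** The opposing case has real force on several points.

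- **The pre-treatment baseline is right for treatment response.** This stands. A reader might infer that the baseline rule is wrong or throws the data away. The documents do not support that: the defect is a missing observation-period analysis and a missing rule for subjects who are never treated.
- **The data are not wholly lost.** This stands in part. Individual values may appear in ITT Listings 16.2.1 and 16.2.2. The documented-growth subgroup in SAP 4.4 sets no time limit on growth, so the separate report under SAP 8.1.8 might use observation scans as history for those who grew. The SAP does not say so, and doing so could leave out non-growers.
- **Context exists elsewhere.** This stands. A reader might take Cohort 10 for a concurrent control without which post-treatment growth cannot be interpreted. No document calls it one, SAP 8.1.8 already uses historical rates, and a cohort enrolled without documented growth is a poor reference for Cohort 12, which requires it.
- **No listed objective depends on it.** Estimating untreated growth appears in the rationale, not among the primary or secondary objectives, and the study is exploratory. This limits the weight of the point but does not remove the stated purpose.
- **The 48 is a ceiling.** It needs six subjects, none growing, all followed for two years. Enrolment closed under Rev-11, and SAP 4.2 moved the final analysis to Week 52 after early termination.

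**Conclusion.** The point holds as a gap in the analysis plan. The SAP contains no table or graph that estimates growth during Cohort 10's observation period, and it leaves never-treated Cohort 10 subjects in the primary ITT population without a baseline, a change or a windowed visit. SAP 8.2 then keeps them out of the visual acuity failures by default.

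The size is modest: at most about 48 assessments, or about 24 if observation was cut at Week 52. That cut is an assumption, because the SAP does not say how Week 52 applies to a subject who was never treated. The number actually enrolled in Cohort 10 and the number who grew are not in the documents.

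The evidence does not support saying that the observation data can never be seen, or that the trial loses its only reference for post-treatment growth. Any estimate would be imprecise descriptive context. The change is still worth making, because the data are already collected and the cost is small.

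**What to change.** 1. **Observation baseline and windows.** For Cohort 10, set an observation baseline at the Screening Visit, with windows at each 90 (±7) days until first treatment or exit. Keep the pre-treatment baseline, under a separate name, for the treated period.
2. **Observation-period summary.** Add a table of change in thickness and LBD and growth rate (mm/year), including non-growers. Show individual slopes, a mixed-model slope using all observation scans, and time to growth or the proportion growing. Do not rely on a plain mean of individual slopes. The mixed model copes better with stopping on growth when the scans behind that decision are in the model. With about 6 subjects its random-effects structure must be simple.
3. **Never-treated subjects in ITT tables.** State that they are shown separately and are not counted as tumor control or vision preservation in the post-treatment ITT summaries or the Cohort 9–12 subtotal.
4. **Link to SAP 8.1.8.** Say whether observation scans serve as history in the separate report and, if so, how non-growers are handled.
5. **Labelling.** SAP v5.0 follows the first database lock, so mark the new output as added after lock, descriptive and based on a small sample, and not as a concurrent control.

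The cost is SAP wording and one or two tables. No new data or clinical rule is involved.
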